### **Data processing and analysis**

One biostatistician who is blinded to interventions will be responsible for statistical analysis. The analysis will be carried out on the intention-to-treat (ITT) population, for which participants have been randomized. A linear mixed-effect model will be applied to compare the primary outcome (changes in total MoCA score from baseline) and secondary outcomes (changes in scores of the Digit span test, MBI, VAS, GDS and ISI), with time (baseline, week 6, and week 12) and group (CAT, CAE, CAT+CAE, and routine care) as categorical fixed factors and random intercepts within a scaled identity covariance matrix. Gender, age, baseline MoCA score, and baseline medication will serve as covariates. Subgroup analysis will be further conducted to compare outcomes by gender, age, and severity of dementia to detect whether these factors are associated with the outcomes. Pairwise comparisons will be further carried out to examine between-group differences. One-way analysis of variance (one-way ANOVA) will be used to detect differences in continuous baseline variables. Categorical baseline variables, including discontinuation and incidence of AEs, will be analyzed using the Chi-square test or Fisher's exact test. Statistical significance was defined as a two-tailed  $P < 0.05$ . The analysis will be conducted using R Studio software.

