- (b) to determine whether other symptoms (e.g., functional independence, pain, depression, and sleep disorder) in the treatment group improve more than in the control group; and
- (c) to investigate whether acupuncture or acupressure is safe for the elderly with cognitive impairment or dementia.

Patient population

Elderly patients with cognitive impairment or dementia are eligible for enrolment.

Inclusion criteria

Subjects will be eligible for this study if they:

- (a) are aged 65 years or above;

- (b) have a clinical diagnosis of any type of dementia or met the criteria of major and mild neurocognitive disorder based on the Fifth Edition of the Diagnostic and Statistical Manual of Mental Disorders (DSM-5);¹ and
- (c) have mild to moderate dementia at a stage of 3 to 5 on the Global Deterioration Scale.²

Exclusion criteria

Subjects will be excluded if they:

- (a) have the severity of dementia with a stage below 3 or above 5 on the Global Deterioration Scale;
- (b) have severe skin lesions on acupuncture and acupressure areas;
- (c) have a significant bleeding tendency;
- (d) have a heart pacemaker or implantable cardioverter defibrillator;
- (e) are currently receiving acupressure as a regular therapy;
- (f) have had surgery on the head or neck; or
- (g) are currently receiving anti-coagulant treatment.

Randomization, central allocation and blindness

One independent research assistant will be in charge of randomization and central allocation as the central coordinator. After confirmation of patients' eligibility and completion of the baseline assessment, participants will be randomly assigned to CAT, CAE, CAT+CAE, or routine care groups in a ratio of 1:1:1:1. Random codes were produced in advance using simple, complete, non-sequential numbers, with a block of 4, 8 and 12, through a random allocation software at <http://mahmoodsaghaei.tripod.com/Softwares/randalloc.html>. Randomization information will be sealed in sequentially numbered opaque envelopes.

Central allocation will be conducted, i.e., site investigators who are responsible for subjects' eligibility will obtain the opaque envelope from the central coordinator for an eligible subject who will be allocated to one of the four groups. Each envelope will be opened by acupuncturists after the participant completes the baseline assessment. Clinical assessors and data analysts will be blind to patients' treatment.

Intervention

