- (c) Marital status (Categories: married or living with partner / single, separated, divorced, or widowed)
- (d) Education level (Categories: uneducated / primary or below / lower secondary / upper secondary / university or above)
- (e) Past occupation (Categories: managers and administrators / professional and associate professional / skilled and semi-skilled worker / unskilled worker / housework / others)
- (f) Type of cognitive impairment (Categories: Alzheimer's disease / vascular dementia / others)
- (g) Past medical history (Categories: cardiometabolic disease / malignant neoplasm / stroke / Parkinson's disease / psychotic disorder / affective disorder)
- (h) Current medication (Categories: cholinesterase inhibitors / glutamate regulators / antidepressants / antipsychotics / hypnotics)

- (i) Baseline MoCA score
- (j) Baseline DSF and DSR scores
- (k) Baseline MBI score
- (l) Baseline VAS score
- (m) Baseline GDS-15 score
- (n) Baseline ISI score

Continuous variables will be presented using mean with standard deviation (SD). One-way analysis of variance (one-way ANOVA) will be used to detect differences in continuous baseline variables.

Categorical variables will be presented by counts with percentages. Percentages will be calculated according to the number of patients for whom data are available. Categorical variables will be analyzed using the Chi-square test or Fisher's exact test.

Discontinuation will be summarized by counts with percentages. Chi-square test or Fisher's exact test will be used to detect differences between the four groups.

Primary outcome

A linear mixed-effect model will be applied to compare the primary outcome (changes in total MoCA score from baseline), with time (baseline, week 6, and week 12) and group (CAT, CAE, CAT+CAE, and routine care) as categorical fixed factors and random intercepts within a scaled identity covariance matrix. Gender, age, baseline MoCA score, and baseline medication will serve as covariates. Pairwise comparisons will be further carried out to examine between-group differences. Two-tailed P-values will be reported in addition to confidence intervals ([Proposed Tables 2 and 3](#)).

Subgroup analysis will be further conducted to compare outcomes to detect whether these subgroup factors are associated with outcomes. The following subgroups include:

- (a) Age (<85 years and \geq 85 years);
- (b) Gender (male and female); and

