- (c) severity of dementia (mild cognitive decline [Stage 3], moderate cognitive decline [Stage 4], moderately severe cognitive decline [Stage 5])

Secondary outcomes

A linear mixed-effect model will be applied to compare the secondary outcomes, including changes in scores of the Digit span test (DSF and DSR), MBI, VAS, GDS and ISI, with time (baseline, week 6, and week 12) and group (CAT, CAE, CAT+CAE, and routine care) as categorical fixed factors and random intercepts within a scaled identity covariance matrix. Gender, age, baseline MoCA score, and baseline medication will serve as covariates.

Pairwise comparisons will be further carried out to examine between-group differences. Two-tailed P-values will be reported in addition to confidence intervals ([Proposed Tables 2 and 3](#)).

Safety outcomes

AEs related to treatment will be tabulated by treatment group without statistical tests or confidence intervals ([Proposed Table 4](#)).

All AEs that occurred throughout the trial will be tabulated by treatment group and AE category (mild, moderate, severe, life-threatening, or death). Chi-square test or Fisher's exact test will be used to detect differences between the four groups ([Proposed Table 5](#)).

Details of serious AEs and death cases will be summarized and listed in a separate table.

Interim analysis

No interim outcome analyses were done prior to the completion of the study to avoid assessment bias.

Missing data

A linear mixed-effect model will be conducted for all analyses of primary and secondary outcomes without imputation of missing data.¹⁶

Proposed Tables

Table 1. Baseline characteristics

Characteristic	CAT (n=62)	CAE (n=62)	CAT+CAE (n=62)	Routine care (n=62)	Total (n=248)	P value
Age, years *	XX ± XX	XX ± XX	XX ± XX	XX ± XX	XX ± XX	XX
Gender (Female) †	XX (XX)	XX (XX)	XX (XX)	XX (XX)	XX (XX)	XX
Marital status †						XX
Married or living with partner	XX (XX)	XX (XX)	XX (XX)	XX (XX)	XX (XX)	
Single, separated, divorced, or widowed	XX (XX)	XX (XX)	XX (XX)	XX (XX)	XX (XX)	
Education level †						XX
Uneducated	XX (XX)	XX (XX)	XX (XX)	XX (XX)	XX (XX)	
Primary or below	XX (XX)	XX (XX)	XX (XX)	XX (XX)	XX (XX)	
Lower Secondary	XX (XX)	XX (XX)	XX (XX)	XX (XX)	XX (XX)	
Upper Secondary	XX (XX)	XX (XX)	XX (XX)	XX (XX)	XX (XX)	
University or above	XX (XX)	XX (XX)	XX (XX)	XX (XX)	XX (XX)	
Past occupation †						XX
Managers and administrators	XX (XX)	XX (XX)	XX (XX)	XX (XX)	XX (XX)	

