Professional and associate professional	XX (XX)	XX (XX)	XX (XX)	XX (XX)	XX (XX)	
Skilled and semi-skilled worker	XX (XX)	XX (XX)	XX (XX)	XX (XX)	XX (XX)	
Unskilled worker	XX (XX)	XX (XX)	XX (XX)	XX (XX)	XX (XX)	
Housework	XX (XX)	XX (XX)	XX (XX)	XX (XX)	XX (XX)	
Others / no information	XX (XX)	XX (XX)	XX (XX)	XX (XX)	XX (XX)	
Type of cognitive impairment †						XX
Alzheimer's disease	XX (XX)	XX (XX)	XX (XX)	XX (XX)	XX (XX)	
Vascular dementia	XX (XX)	XX (XX)	XX (XX)	XX (XX)	XX (XX)	
Others ‡	XX (XX)	XX (XX)	XX (XX)	XX (XX)	XX (XX)	
Past medical history †						
Cardiometabolic disease	XX (XX)	XX (XX)	XX (XX)	XX (XX)	XX (XX)	XX
Malignant neoplasm	XX (XX)	XX (XX)	XX (XX)	XX (XX)	XX (XX)	XX
Stroke	XX (XX)	XX (XX)	XX (XX)	XX (XX)	XX (XX)	XX
Parkinson's disease	XX (XX)	XX (XX)	XX (XX)	XX (XX)	XX (XX)	XX
Psychotic disorder	XX (XX)	XX (XX)	XX (XX)	XX (XX)	XX (XX)	XX
Affective disorder	XX (XX)	XX (XX)	XX (XX)	XX (XX)	XX (XX)	XX
Current medication †						
Cholinesterase inhibitors	XX (XX)	XX (XX)	XX (XX)	XX (XX)	XX (XX)	XX
Glutamate regulators	XX (XX)	XX (XX)	XX (XX)	XX (XX)	XX (XX)	XX
Antidepressants	XX (XX)	XX (XX)	XX (XX)	XX (XX)	XX (XX)	XX
Antipsychotics	XX (XX)	XX (XX)	XX (XX)	XX (XX)	XX (XX)	XX
Hypnotics	XX (XX)	XX (XX)	XX (XX)	XX (XX)	XX (XX)	XX
MoCA *	XX ± XX	XX ± XX	XX ± XX	XX ± XX	XX ± XX	XX
DSF *	XX ± XX	XX ± XX	XX ± XX	XX ± XX	XX ± XX	XX
DSR *	XX ± XX	XX ± XX	XX ± XX	XX ± XX	XX ± XX	XX
MBI *	XX ± XX	XX ± XX	XX ± XX	XX ± XX	XX ± XX	XX

Characteristic	CAT (n=62)	CAE (n=62)	CAT+CAE (n=62)	Routine care (n=62)	Total (n=248)	P value
VAS *	XX ± XX	XX ± XX	XX ± XX	XX ± XX	XX ± XX	XX
GDS *	XX ± XX	XX ± XX	XX ± XX	XX ± XX	XX ± XX	XX
ISI *	XX ± XX	XX ± XX	XX ± XX	XX ± XX	XX ± XX	XX

Abbreviations: CAT, comprehensive acupuncture therapy; CAE, Comfy Acupressure for the Elderly; DSF, Digit Span Forward; DSR, Digit Span Reverse; MoCA, Montreal Cognitive Assessment; MBI, Modified Barthel Index; VAS, Visual Analogue Scale; GDS, Geriatric Depression Scale; ISI, Insomnia Severity Index.

* Continuous data are expressed as mean ± SD and were examined using One-way ANOVA. Those which statistical differences $P<0.05$ reached the significance level are indicated in bold font.

† Categorical data are expressed as count (percentage) and were examined using Chi-square (χ^2) or Fisher Exact test. Those which statistical differences $P<0.05$ reached the significance level are indicated in bold font.

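### The SAP splits age at an unexplained 85 for the subgroup analysis although age is collected in years; if the treatment effect changes roughly linearly with age, the split discards information that a continuous term would keep

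*SAP*

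**What the plan says.** The protocol (Data processing and analysis) names the subgroup factors without defining them: "Subgroup analysis will be further conducted to compare outcomes by gender, age, and severity of dementia". The SAP (Primary outcome) adds the definitions. Its age item reads "a) Age (<85 years and" 85 and over, and no reason is given. The stated purpose is "Subgroup analysis will be further conducted to compare outcomes to detect whether these subgroup factors are associated with outcomes"; no arm-by-age term is written down.

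Elsewhere age is treated as continuous. Proposed Table 1 of the SAP lists it in years, and the table's footnote says "Continuous data are expressed as mean ± SD and were examined using One-way ANOVA". Entry is open to people who "are aged 65 years or above", with no upper limit.

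For the main model the SAP says "Gender, age, baseline MoCA score, and baseline medication will serve as covariates". Only time and group are specified "as categorical fixed factors and random intercepts within a scaled identity covariance matrix". It is a fair inference that age enters that model in years, but the SAP does not say so.

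**The concern.** A two-group split treats a 65-year-old and an 84-year-old as the same, and an 84-year-old and an 85-year-old as different. If benefit rises or falls gradually with age, variation within each group is discarded and a real gradient is easier to miss. The answer also depends on where the cut falls, and a reader cannot tell why it falls at 85. What is at stake is the quality of a supportive subgroup analysis in a trial sized only for a pairwise difference between arms. The primary result is not at stake.

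**Working it through.** **Inputs from the documents** (SAP, Sample size determination): mean difference M = 2.1 MoCA points, SD = 3.6, constant 7.9 (two-sided 5%, 80% power), 62 per arm, 25% dropout.

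**The plan's own figure.** n = 2/(2.1/3.6)² × 7.9 = 46.4 per arm, and 46.4/0.75 = 61.9, so 62. This reproduces. Expected completers are 62 × 0.75 = 46.5 per arm. The plan gives no figure for any subgroup or interaction.

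**Assumptions not in the documents.** The treatment effect changes linearly with age, and age follows either a normal or a uniform distribution. Let q be the share aged 85 or over.

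**Information kept by the split.** This is the squared correlation r² between age and the 85-or-over indicator.

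- Normal age: r² = φ(z)²/[q(1−q)], where z is the cut with a share q above it. For q = 0.5, 0.3989²/0.25 = 0.637. For q = 0.2, 0.2800²/0.16 = 0.490.
- Uniform age: r² = 3q(1−q). For q = 0.5, 3 × 0.25 = 0.75. For q = 0.2, 3 × 0.16 = 0.48.

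**Power after the split**, for a single two-arm (1-df) contrast that has 80% power on continuous age: Φ[(1.96 + 0.8416) × r − 1.96].

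| Share aged 85 or over | Kept, normal | Kept, uniform | Power, normal | Power, uniform |
|---|---|---|---|---|
| 50% | 0.64 | 0.75 | 61% | 68% |
| 30% | 0.58 | 0.63 | 57% | 60% |
| 20% | 0.49 | 0.48 | 50% | 49% |
| 10% | 0.34 | 0.27 | 37% | 31% |

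The 49-68% range therefore belongs to shares of 20% to 50%; it is not a bound. With normal or uniform age the formulas are symmetric, so 20% to 80% aged 85 or over gives the same range. At 20%, the older group has 46.5 × 0.2 = about 9 completers per arm.

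**Check by simulation** (two arms, 62 per arm, SD 3.6, 3,000 runs, normal age with SD 7 truncated to 65-105). Power on continuous age against the split was 77% against 58% with the age distribution centred at 85, 75% against 53% at 82, and 72% against 43% at 79. The ordering and rough size agree with the formula.

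**How large a gradient this supposes.** The standard error of the difference in slopes between two arms, per SD of age, is 3.6 × √(2/46.5) = 0.747. Eighty per cent power needs 2.80 × 0.747 = 2.1 MoCA points per SD of age. At half that gradient (1.05 per SD), power is 29% on continuous age and 16-23% after the split. At 0.5 per SD it is about 10% against 7.5-9%.

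**The case against.** **The loss is conditional.** A reader might infer that the plan, as written, throws away a quarter to a half of the information. The documents do not support that as a property of the plan. The figure needs a roughly linear gradient and about 20% to 80% of participants aged 85 or over, and the documents give no age distribution. With fewer aged 85 or over the loss exceeds a half; if the effect truly steps at 85, the split loses nothing. This objection stands, and the figures are given only conditionally.

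**The SAP names no interaction.** It speaks of factors being associated with outcomes, so a calculation about effect modification presupposes a test that it does not specify. This also stands. The missing term is a separate gap, and the fix has to write the term down as well as change the coding.

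**The benchmark is generous.** A gradient of 2.1 points per SD equals the entire assumed treatment effect. For smaller gradients both codings have low power and the difference between them shrinks. This stands and limits the practical gain.

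**There are four arms.** An overall arm-by-age test has 3 df; if it had 80% power on continuous age, it would have about 46-66% after the split. The 49-68% range is for one two-arm contrast only.

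**The cut is written into the SAP.** That limits data-driven choice of a cut, which is a genuine merit. It does not explain 85 or recover the discarded information, and the cut can be kept for display.

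**Dementia stage.** One might extend the point to "severity of dementia (mild cognitive decline [Stage 3], moderate cognitive decline [Stage 4], moderately severe cognitive decline [Stage 5" and ask for a linear trend. The documents do not support going that far. These are named levels of the eligibility scale, the SAP does not rule out a trend, equal spacing of the stages would itself be an assumption, and no loss has been calculated. No change is asked for there.

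**Conclusion.** The point holds as a low-cost improvement to an exploratory analysis. The SAP divides a variable collected in years at an unexplained 85. Under a linear gradient, the split keeps about 64-75% of the information when half the participants are 85 or over, about 48-49% when 20% are, and less below that. For a single two-arm contrast with 80% power on continuous age, power falls to about 49-68% across those shares. This rests on assumed normal or uniform age distributions, on linearity, and on a gradient of about 2.1 MoCA points per SD of age, given the plan's SD of 3.6 and 46.5 completers per arm. The subgroup analysis is weak under either coding, and the comparison of arms on MoCA does not depend on this choice.

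**What to change.** In the SAP's subgroup paragraph under Primary outcome, state that effect modification by age will be tested with an arm-by-age term, age in years and continuous, at Week 12. Keep the under-85 and 85-and-over groups only to display between-arm estimates with 95% CIs, and label the analysis exploratory. It would also help to state the form in which age enters the main model, since that is now left to inference.

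The cost is a sentence or two in the SAP and no new data. It does add an interaction test that the SAP does not now name. The downside is that a linear term is less sensitive than the split if the effect really jumps at 85; the retained display would still show such a step.

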Abbreviations: CAT, comprehensive acupuncture therapy; CAE, Comfy Acupressure for the Elderly; DSF, Digit Span Forward; DSR, Digit Span Reverse; GDS, Geriatric Depression Scale; ISI, Insomnia Severity Index; MBI, Modified Barthel Index; MoCA, Montreal Cognitive Assessment; VAS, Visual Analogue Scale.

* A greater positive value represents improvement in symptoms.

† A greater negative value represents improvement in symptoms.

‡ *P* value was calculated using a mixed-effects model with baseline adjustment to illustrate between-group differences. Those which statistical differences $p<0.05$ reached significance level are indicated in bold font.

Table 3. Intra-group comparison in outcomes

Outcomes	Change from baseline							
	CAT (n=62)		CAE (n=62)		CAT+CAE (n=62)		Routine care (n=62)	
	Mean (95%CI)	P value [‡]	Mean (95%CI)	P value [‡]	Mean (95%CI)	P value [‡]	Mean (95%CI)	P value [‡]
Primary outcome								
MoCA *								
Week-6	XX (XX, XX)	XX	XX (XX, XX)	XX	XX (XX, XX)	XX	XX (XX, XX)	XX
Week-12	XX (XX, XX)	XX	XX (XX, XX)	XX	XX (XX, XX)	XX	XX (XX, XX)	XX
Secondary outcomes								
DSF *								
Week-6	XX (XX, XX)	XX	XX (XX, XX)	XX	XX (XX, XX)	XX	XX (XX, XX)	XX
Week-12	XX (XX, XX)	XX	XX (XX, XX)	XX	XX (XX, XX)	XX	XX (XX, XX)	XX
DSR *								
Week-6	XX (XX, XX)	XX	XX (XX, XX)	XX	XX (XX, XX)	XX	XX (XX, XX)	XX
Week-12	XX (XX, XX)	XX	XX (XX, XX)	XX	XX (XX, XX)	XX	XX (XX, XX)	XX
MBI *								
Week-6	XX (XX, XX)	XX	XX (XX, XX)	XX	XX (XX, XX)	XX	XX (XX, XX)	XX
Week-12	XX (XX, XX)	XX	XX (XX, XX)	XX	XX (XX, XX)	XX	XX (XX, XX)	XX
VAS †								
Week-6	XX (XX, XX)	XX	XX (XX, XX)	XX	XX (XX, XX)	XX	XX (XX, XX)	XX
Week-12	XX (XX, XX)	XX	XX (XX, XX)	XX	XX (XX, XX)	XX	XX (XX, XX)	XX
GDS †								
Week-6	XX (XX, XX)	XX	XX (XX, XX)	XX	XX (XX, XX)	XX	XX (XX, XX)	XX
Week-12	XX (XX, XX)	XX	XX (XX, XX)	XX	XX (XX, XX)	XX	XX (XX, XX)	XX
ISI †								
Week-6	XX (XX, XX)	XX	XX (XX, XX)	XX	XX (XX, XX)	XX	XX (XX, XX)	XX
Week-12	XX (XX, XX)	XX	XX (XX, XX)	XX	XX (XX, XX)	XX	XX (XX, XX)	XX

Abbreviations: CAT, comprehensive acupuncture therapy; CAE, Comfy Acupressure for the Elderly; DSF, Digit Span Forward; DSR, Digit Span Reverse; GDS, Geriatric Depression Scale; ISI, Insomnia Severity Index; MBI, Modified Barthel Index; MoCA, Montreal Cognitive Assessment; VAS, Visual Analogue Scale.

* A greater positive value represents improvement in symptoms.

† A greater negative value represents improvement in symptoms.

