‡ P value was calculated using a mixed-effects model with baseline adjustment to illustrate pre- and post-treatment within-group differences. Those which statistical differences $p<0.05$ reached significance level are indicated in bold font

Table 4. Adverse events related to treatment, n (%)^{*}

Adverse event	CAT (n = 62)	CAE (n = 62)	CAT+CAE (n = 62)
Bleeding at the site of needling	XX (XX)	XX (XX)	XX (XX)
Hematoma around the site of needling	XX (XX)	XX (XX)	XX (XX)
Dizziness after treatment	XX (XX)	XX (XX)	XX (XX)
Headache after treatment	XX (XX)	XX (XX)	XX (XX)
Localized pain	XX (XX)	XX (XX)	XX (XX)
Needle phobia	XX (XX)	XX (XX)	XX (XX)

Abbreviations: CAT, comprehensive acupuncture therapy; CAE, Comfy Acupressure for the Elderly.

* Data was expressed as number of patients (%).

Table 5. Reported adverse events in different categories, n (%)^{*}

Adverse Event Category	CAT (n=62)	CAE (n=62)	CAT+CAE (n=62)	Routine care (n=62)	P-value*
Any	XX (XX)	XX (XX)	XX (XX)	XX (XX)	XX
Mild	XX (XX)	XX (XX)	XX (XX)	XX (XX)	XX
Moderate	XX (XX)	XX (XX)	XX (XX)	XX (XX)	XX
Severe	XX (XX)	XX (XX)	XX (XX)	XX (XX)	XX
Life-threatening	XX (XX)	XX (XX)	XX (XX)	XX (XX)	XX
Death	XX (XX)	XX (XX)	XX (XX)	XX (XX)	XX

Abbreviations: CAT, comprehensive acupuncture therapy; CAE, Comfy Acupressure for the Elderly.

* Data was expressed as number of patients (%). Those which statistical differences $p < 0.05$ reached significance level are indicated in bold font.

[figure not shown]

Figure 1. CONSORT Flowchart

References

1. American Psychiatric Pub. Diagnostic and Statistical Manual of Mental Disorders (DSM-5®). American Psychiatric Pub; 2013.

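### The secondary-outcome model names only baseline MoCA and keeps an all-zero baseline row: fitted as written, it loses precision in one contrast and understates the standard error in another

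*SAP*

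**What the plan says.** SAP, Secondary outcomes, defines the responses as "including changes in scores of the Digit span test (DSF and DSR), MBI, VAS, GDS and ISI". The model is fitted "with time (baseline, week 6, and week 12) and group (CAT, CAE, CAT+CAE, and routine care) as categorical fixed factors", with random intercepts and a scaled identity covariance. The covariates follow: "Gender, age, baseline MoCA score, and baseline medication will serve as covariates". The same sentence closes the model description under SAP, Primary outcome, where baseline MoCA is the outcome's own baseline. Protocol, Data processing and analysis, gives one list for the primary outcome and for "secondary outcomes (changes in scores of the Digit span test, MBI, VAS, GDS and ISI".

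The primary model has the same time levels: "compare the primary outcome (changes in total MoCA score from baseline), with time (baseline, week 6, and week 12".

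The footnote to Proposed Table 2 says that the P "value was calculated using a mixed-effects model with baseline adjustment to illustrate between-group differences". The footnote to Proposed Table 3 says that the P "value was calculated using a mixed-effects model with baseline adjustment to illustrate pre- and post-treatment within-group differences". Neither names the baseline variable.

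The own baselines are available. SAP, Demographic characteristics and baseline comparisons, lists "Baseline DSF and DSR scores" and the baselines of the other four scales, and Protocol Table 3 schedules all of them at enrolment.

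**The concern.** A covariate list that is right for MoCA has been carried over to six outcomes for which it leaves out the most useful covariate. A change score subtracts its own baseline with coefficient 1. With equal SDs and a correlation below 1, that over-corrects chance imbalance and adds avoidable variance.

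The time factor is a second problem. The response is change from baseline, so the baseline row is zero for every participant. That row carries no information on treatment, but it enters the estimate of the model's variance.

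The SAP's second aim, on function, pain, mood and sleep, rests on these outcomes. Two analysts following the same text could report different intervals and P values.

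**Working it through.** **The plan's own figure.** The only sample size is for MoCA: 2/(2.1/3.6)² × 7.9 = 46.4 per arm, and 46.4/0.75 = 61.9, the stated 62. It reproduces. The documents give no power or SD for any secondary outcome.

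**Inputs.** The documents give the response, the time levels, the random intercept and the covariates. The correlation ρ between visits (equal for all pairs) and equal SDs, scaled to 1, are assumptions. Data are complete unless stated. Variances are per participant.

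**The two contrasts.** The model text names time and group but no interaction. Proposed Table 2 reports separate week-6 and week-12 differences, so one is implied. The week-12 result could be taken as the group-by-time contrast (week 12 minus baseline, between arms) or as the group contrast at week 12. Without covariates and with complete data the two estimates are identical, because the baseline row is zero. Their standard errors are not.

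**Step 1: precision of the group-by-time contrast.** A covariate constant over time cancels when week 12 is compared with baseline. Neither baseline MoCA nor an own baseline merely added to the list changes this contrast. As written, the variance is 2(1−ρ). With follow-up rows only and own-baseline adjustment it is 1−ρ². The ratio is (1+ρ)/2.

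| ρ (assumed) | 2(1−ρ) | 1−ρ² | Ratio | Variance saved | Interval narrower by |
|---|---|---|---|---|---|
| 0.5 | 1.00 | 0.75 | 0.75 | 25% | 13% |
| 0.7 | 0.60 | 0.51 | 0.85 | 15% | 8% |
| 0.9 | 0.20 | 0.19 | 0.95 | 5% | 2.5% |

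A comparison with 80% power when adjusted would have about 68%, 73% and 78% as written. In a simulation with 62 per arm and 25% random dropout (half before week 6, assumed), the variance saved was 25%, 13% and 6%, and mean estimates stayed within 0.005 of zero.

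**Step 2: unequal SDs.** Let k be the week-12 SD divided by the baseline SD. The ratio becomes k²(1−ρ²)/(1+k²−2ρk). At ρ = 0.8:

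- k = 1.25: 1.5625 × 0.36/(1 + 1.5625 − 2) = 0.5625/0.5625 = 1.00, so no gain.
- k = 0.8: 0.64 × 0.36/(1 + 0.64 − 1.28) = 0.2304/0.36 = 0.64, so a 36% gain.

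**Step 3: standard error of the week-12 group contrast.** The three rows have variances 0, 2(1−ρ) and 2(1−ρ). Their covariances are 0, 0 and 1−ρ. A random intercept with one residual variance averages these:

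- intercept variance: (1−ρ)/3
- residual variance: (4/3)(1−ρ) − (1−ρ)/3 = 1−ρ
- variance used for the week-12 contrast: (4/3)(1−ρ)
- true week-12 variance: 2(1−ρ)

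The standard error is therefore √(2/3) = 0.816 of its correct value. The nominal 1.96 acts as 1.96 × 0.816 = 1.60, and two-sided type I error is about 11% at any ρ. Simulations with 47 per arm and equal SDs gave about 10-12%. The group-by-time contrast uses twice the residual variance, 2(1−ρ), which is correct, and its simulated error stayed near 5%.

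**Step 4: primary MoCA.** With the own baseline listed and the zero row kept, the model's week-12 variance is (4/3)(1−ρ) − (4/9)(1−ρ)² and the true one is 2(1−ρ) − (8/9)(1−ρ)². At ρ = 0.5 these are 0.556 and 0.778, and at ρ = 0.9 they are 0.129 and 0.191. Type I error is about 10% and 11%.

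**The case against.** **The footnotes may already settle it.** They apply baseline adjustment to every row of Tables 2 and 3, and own baseline is a natural reading. A reader might infer that the plan certainly omits it; the documents do not support that. But baseline MoCA also fits the phrase and is the only baseline score that the model text names. Even on the favourable reading, the retained baseline row stops the covariate from helping the group-by-time contrast.

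**The gain may be small.** This stands in part. At ρ = 0.9 it is 5% of the variance, and with a larger week-12 SD it can vanish. Baseline MoCA may also be a partial proxy, most plausibly for digit span, since MoCA also scores attention. At an assumed correlation of 0.6 between the two baselines, the saving in the week-12 group contrast falls to about 19%, 11% and 3% at ρ = 0.5, 0.7 and 0.9. No sample-size claim rests on these outcomes.

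**Stronger readings.** A reader might infer biased treatment effects. Under randomization they are unbiased on average. The over-correction of chance imbalance is not an additional harm: it is the extra variance itself, since 2(1−ρ) − (1−ρ²) = (1−ρ)². A reader might also infer that type I error is inflated throughout. That holds only for the week-12 group contrast, and the documents do not say which contrast will be reported. For the same reason, the opposite inference, that lost precision is the only cost, is not safe either.

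**Conclusion.** The point holds and should be settled before analysis. The secondary model text names only baseline MoCA, the footnotes leave the baseline unnamed, and baseline is a level of time for a response that is zero there.

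Fitted as the text reads, the consequence depends on the contrast:

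- **Group-by-time:** valid, but with avoidable variance of about 25%, 15% and 5% of the as-written variance at ρ = 0.5, 0.7 and 0.9 with equal SDs. At ρ = 0.8 the figure runs from nil to 36% as the SD ratio goes from 1.25 to 0.8.
- **Week-12 group contrast:** standard errors too small, with two-sided type I error of about 10-12% under equal SDs and equal visit correlations. This applies to the primary MoCA model too, although its own baseline is already listed.

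The documents give neither ρ nor the SDs, so the sizes are illustrative. The mismatch between model text and footnotes, and the zero row, do not depend on them.

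**What to change.** In SAP, Primary outcome and Secondary outcomes, and in Protocol, Data processing and analysis, specify one model for every outcome. The response is change from baseline at week 6 and week 12. Fixed effects are group, time (those two visits), group-by-time, the baseline of the outcome being analysed, that baseline by time, gender, age and baseline medication. Each participant has a random intercept. Baseline MoCA may stay as an extra covariate for the secondary outcomes.

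The baseline-by-time term is needed if correlations differ by visit. With assumed values of 0.7 (baseline to week 6), 0.5 (baseline to week 12) and 0.7 (week 6 to week 12), the week-12 estimate keeps a slope of about −0.10 on baseline imbalance without the term and about 0.00 with it.

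Change both footnotes to *adjusted for the baseline score of the outcome shown in the row*, and state that the Table 3 changes are adjusted means from this model.

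The cost is a few model terms and no new data. Participants with no follow-up contribute no row although they belong to the ITT population. At 25% dropout this is at most about 15 of 62 per arm (0.25 × 62 = 15.5), if all leave before week 6. Count them in the table. If the sponsor wants to keep them, model raw scores at all three visits with group means constrained equal at baseline and an unstructured covariance. With a random intercept alone, that model left a slope of about −0.13 in the same unequal-correlation setting, against 0.00 with the unstructured covariance.
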